6.11.7.4. Hepatobiliary Events

6.11.7.4.1. Treatment-Emergent Potential Hepatic Disorder

The percentages of patients with treatment-emergent drug-related hepatic disorder events will be summarized and compared by treatment group using MedDRA PT nested within each SMQ, and ordered by decreasing frequency. The following SMQs based on MedDRA will be used to identify potential hepatic disorders:

- Broad and narrow terms in the Liver related investigations, signs and symptoms SMQ (20000008)
- Broad and narrow terms in the Cholestasis and jaundice of hepatic origin SMQ (20000009)
- Broad and narrow terms in the Hepatitis non-infections SMQ (20000010)
- Broad and narrow terms in the Hepatic failure, fibrosis and cirrhosis and other liver damage SMQ (20000013)
- Narrow terms in the Liver-related coagulation and bleeding disturbances SMQ (20000015)

The percentage of patients with any 1 of the terms will be summarized, in addition to the percentages for each MedDRA PT. The percentages of patients with potentially drug-related hepatic disorders that lead to permanent study discontinuation will be summarized similarly.

6.11.7.5. Malignant Neoplasm Events

The Malignant tumors SMQ will be used to identify treatment-emergent malignant neoplasm event.

6.11.8. Blood Ketones

Blood ketones should be tested with the meter provided when unexplained hyperglycemia occurs with blood glucose >250 mg/dL (13.9 mmol/L) or a pump occlusion alarm occurs with blood glucose >250 mg/dL (13.9 mmol/L). If a test is performed, ketone values should be documented in the eCRF and will be presented by (≤ 0.6 mmol/L, >0.6 mmol/L) for each treatment group. There will be no statistical comparison between treatments.

6.11.9. Clinical Laboratory Evaluation

The data from safety laboratory measures will be only collected at Visit 1 and Visit 2 for patient safety. Therefore no by-treatment group summary or statistical analysis will be provided.

6.11.10. Vital Signs and Other Physical Findings

Post-baseline measurements and change from baseline to post-baseline for vital signs (systolic blood pressure [SBP], diastolic blood pressure [DBP], pulse rate) and physical characteristics (weight, BMI) at the scheduled visits will be summarized by week (relative to the start of each randomized treatment period) for patients who have both baseline and at least 1 post-baseline result.

The measurements during the treatment period (0-12 weeks) will be analyzed by MMRM model with treatment, baseline value of the response variable, sequence, period, week (defined from the start of each randomized treatment period), and week by treatment interaction as fixed factors and patient as the random factor.

Change from the minimum value during the baseline period to the minimum value during the 2 randomized treatment periods for vital signs and physical characteristics will be summarized by treatment group for patients who have both baseline and at least 1 post-baseline result. Baseline will be the minimum of nonmissing observations in the baseline period. The minimum value in the treatment period will be analyzed. Similarly, change from the maximum value during the baseline period to the maximum value during each of the 2 randomized treatment periods (Period I and Period II) for vital signs and physical characteristics will be summarized by treatment group for patients who have both baseline and at least 1 post-baseline result. Baseline will be the maximum of nonmissing observations in the baseline period. The maximum value in the treatment period will be analyzed. Planned and unplanned measurements will be included in the analysis.

The percentages of patients with treatment-emergent high or low vital signs and weight at any time after randomization during each of the 2 randomized treatment periods (Period I and Period II) will be summarized and compared between treatment groups using Prescott's exact test for patients who have both baseline and at least 1 postbaseline measurement. A treatment-emergent high result is defined as a change from a value less than or equal to the high limit at all baseline

visits to a value greater than the high limit at any time that meets the specified change criteria during the 2 randomized treatment periods. A treatment-emergent low result is defined as a change from a value greater than or equal to the low limit at all baseline visits to a value less than the low limit at any time that meets the specified change criteria during the 2 randomized treatment periods. Table ITSI.6.7 will be used to define the low and high limits and change thresholds.

Table ITSI.6.7. Categorical Criteria for Abnormal Treatment-Emergent Blood Pressure and Pulse Measurement, and Categorical Criteria for Weight Changes for Adults

Parameter	Low	High
Systolic BP (mm Hg) (Supine or sitting – forearm at heart level)	≤ 90 and decrease from baseline ≥ 20	≥ 140 and increase from baseline ≥ 20
Diastolic BP (mm Hg) (Supine or sitting – forearm at heart level)	≤ 50 and decrease from baseline ≥ 10	≥ 90 and increase from baseline ≥ 10
Pulse (bpm) (Supine or sitting)	< 50 and decrease from baseline ≥ 15	> 100 and increase from baseline ≥ 15
Weight (kg) (Consistent clothing and timing in relationship to meals and voiding)	(Loss) decrease $\geq 7\%$	(Gain) increase $\geq 7\%$

Abbreviations: BP = blood pressure.

6.11.11. Immunogenicity

Blood samples for immunogenicity testing will be collected to determine antibody production against insulin lispro for all enrolled patients since Visit 2 prior to the first dose of study-provided insulin treatment. Therefore, the blood sample result at Visit 2 will be considered as the anti-insulin lispro level at baseline for this study.

6.11.11.1. Treatment-Emergent Anti-Insulin Lispro Antibody

The treatment-emergent anti-insulin lispro antibody (denoted as treatment-emergent antidrug antibody [TEADA] throughout this SAP) is based on the change from baseline (Visit 2) to post-baseline (post-Visit 2) in the anti-insulin lispro antibody level (percent binding). Treatment-emergent antidrug antibody can be sub-classified as either treatment-induced (not detected anti-insulin lispro antibody at baseline) or treatment-boosted (detected anti-insulin antibody at baseline):

- treatment-induced response: change from not detected anti-insulin lispro at baseline (Visit 2) to post-baseline detected anti-insulin lispro;
- treatment-boosted response: change from detected anti-insulin lispro at baseline (Visit 2) to post-baseline detected anti-insulin lispro antibody level (percent binding) at least 157% of the baseline value.

The TEADA status during a specific analysis period will be determined using all data in the corresponding analysis period regardless of IP use. The summary for TEADA status and the anti-insulin lispro antibody level will use the same analysis data.

The number and percentage of patients with positive TEADA response during the study (from Visit 2 to Visit 801) will be summarized for the Safety Population overall. For patients with positive TEADA response any time during the study, the number and percentage of patients with positive insulin cross-reactivity anytime during the study, and the number and percentage of patients not meeting the TEADA criteria at Visit 801 will also be summarized for overall. No statistical comparisons between treatment groups will be conducted because patients were exposed to both LY900014 and Humalog due to the crossover design.

The anti-insulin lispro antibody level in percent binding will be summarized by scheduled visit prespecified in the protocol for patients with positive TEADA response from Visit 2 to Visit 801.

A listing of anti-insulin lispro antibody at each visit will be provided. The listing will include anti-insulin lispro antibody status (detected/not detected), anti-insulin lispro antibody percent binding, TEADA status (positive/negative), insulin cross-reactivity status, and insulin cross-reactivity percent binding for the Safety Population.

6.11.12. Patient Narratives

Patient narratives will be provided for all patients in the study who experience any of the following “notable” events prior to data cutoff for the submission:

- deaths
- SAEs
- discontinuations from study (or study drug) due to AEs
- pregnancy

A list of patients who meet the criteria for narratives will be provided.

6.12. CGM Analyses

The analyses described in Section 6.12 will include data collected from first dose to last dose of study drug (i.e., open-label insulin lispro used during the lead-in period or IP used during each of the randomized treatment periods [Period I and Period II]), excluding data (if any) that are collected while patients temporarily are off pump or off study treatment.

All of the variables will be derived for the lead-in period, Period I and Period II. For the lead-in period, the variables will be derived based upon the data collected during the 2-week open-label lispro treatment period. For Period I and Period II, the variables will be derived for 0-4, 0-6, and 4-6 weeks relative to the start of each randomized treatment period, respectively. For the interstitial glucose reduction rate, treatment comparisons will be based upon the derived outcome variables for 0-6 weeks. For other variables, treatment comparisons will be based upon the derived outcome variables for 4-6 weeks.

Table ITSI.6.8 lists all numerical measures for CGM data, including all secondary and exploratory CGM outcome variables.

To ensure that the CGM outcome variables are only calculated from CGM session days with sufficient data within the 24-hour, daytime (0600 hours to midnight), or nighttime (midnight to 0600 hours) periods, the following criteria will be used to determine a valid CGM session day to be counted into the calculation for a visit: 1) minimum number of measures per day – at least 70% of the total measures that are supposed to be obtained (for example, 70% of the 288 measures for the 24-hour period or 70% of 72 measures for the nighttime period); 2) maximum allowable missing interval – no interval greater than 3 hours between non-missing measures.

Similarly, for the by-meal outcome variables, the following criteria will be used to determine a valid CGM session day for a visit: 1) minimum number of measures per day – at least 70% of the total measures that are supposed to be obtained. For example, 70% of the 24 measures for the $iAUC_{0-2hr}$ after breakfast; 2) maximum allowable missing interval – no interval greater than 20 minutes between non-missing measures for the outcome variables using ≤ 2 -hour of CGM data (including $iAUC_{0-1hr}$, $iAUC_{0-2hr}$, average glucose excursions 0-1 or 0-2 hours and time in ranges 0-1 or 0-2 hours after breakfast), and 25 minutes for other by-meal outcome variables.

The definition and derivation of these variables are described in detail in 9.1.

Table ITSI.6.8. Outcome Measures of CGM DATA

Category	Endpoints	24-Hour	Daytime ¹	Nighttime ²	Breakfast ³
Interstitial Glucose Reduction Rate following a Correction Bolus via the Pump (mg/dl/min and mg/dl) ⁴					
	Interstitial glucose reduction rate (glucose reduction [mg/dL and mmol/L] per minute) within 4 hours following a non-meal-related correction bolus via the pump, from hyperglycemia (interstitial glucose >180 mg/dL (10.0 mmol/L) to recovery (interstitial glucose \leq 180 mg/dL)	across all non-meal-related correction doses via the pump			
	Interstitial glucose reduction rate (glucose reduction [mg/dL and mmol/L] per minute) within 4 hours following a non-meal-related correction bolus via the pump, from hyperglycemia (interstitial glucose >180 mg/dL [10.0 mmol/L] and \leq 250 mg/dL [13.9 mmol/L]) to recovery (interstitial glucose \leq 180 mg/dL)	across all non-meal-related correction doses via the pump			

Category	Endpoints	24-Hour	Daytime ¹	Nighttime ²	Breakfast ³
	Interstitial glucose reduction rate (glucose reduction [mg/dL and mmol/L] per minute) within 4 hours following a non-meal-related correction bolus via the pump, from hyperglycemia (interstitial glucose >250 mg/dL [13.9 mmol/L] and ≤300 mg/dL [16.7 mmol/L]) to recovery (interstitial glucose ≤180 mg/dL)	across all non-meal-related correction doses via the pump			
	Interstitial glucose reduction rate (glucose reduction [mg/dL and mmol/L] per minute) within 4 hours following a non-meal-related correction bolus via the pump, from hyperglycemia (interstitial glucose >300 mg/dL [16.7 mmol/L] to recovery (interstitial glucose ≤180 mg/dL)	across all non-meal-related correction doses via the pump			
Incremental AUCs (iAUCs) after Meals					
	iAUC _{0-1hr}				x
	iAUC _{0-2hr}				x
Average Glucose Excursions					
	average glucose excursion 0 to 1 hours				x
	average glucose excursion 0 to 2 hours				x
Glucose in the Target Ranges					
	Duration (in minutes) and percentage of time with glucose values within target range 71 to 180 mg/dL [3.9 and 10.0 mmol/L], both inclusive	x	x	x	x ⁵
	Duration (in minutes) and percentage of time with glucose values within target range 71 to 140 mg/dL [3.9 and 7.8 mmol/L], both inclusive	x	x	x	x ⁵
	Duration (in minutes) and percentage of time with glucose values ≤180 mg/dL [10.0 mmol/L]	x	x	x	x ⁵
Hypoglycemic Episodes					
	Duration (in minutes) and percentage of time with glucose values <50, <60, and ≤70 mg/dL of hypoglycemic episodes, defined as at least 10 consecutive minutes <50, <60, and ≤70 mg/dL [2.8, 3.3, and 3.9 mmol/L]	x	x	x	x ⁵

Category	Endpoints	24-Hour	Daytime ¹	Nighttime ²	Breakfast ³
	Rate (events/patient/year and/or events/patient/30 days) and incidence (percent of patients with at least 1 event) of hypoglycemic episodes, defined as at least 10 consecutive minutes <50, <60, and ≤70 mg/dL [2.8, 3.3, and 3.9 mmol/L]	x	x	x	
Hyperglycemic Episodes					
	Duration (in minutes) and percentage of time with glucose values >180, >250, and >300 mg/dL [10.0, 13.9, and 16.6 mmol/L] and hyperglycemic episodes, defined as at least 10 consecutive minutes >180, >250, and >300 mg/dL [10.0, 13.9, and 16.6 mmol/L]	x	x	x	x ⁵
	Rate (events/patient/year and/or events/patient/30 days) and incidence (percent of patients with at least 1 event) of hyperglycemic episodes, defined as at least 10 consecutive minutes >180, >250, and >300 mg/dL [10.0, 13.9, and 16.6 mmol/L]	x	x	x	
Daily CGM Data Summary					
	Average glucose level	x	x	x	
	Median glucose level	x	x	x	
Glucose Variability and Risk Assessment					
Within-Day	CV	x	x	x	
	SD	x	x	x	
	IQR	x	x	x	
	MAGE	x	x	x	
	LBGI: frequency and extent of low BG readings	x	x	x	
	HBGI: frequency and extent of high BG readings	x	x	x	
	BGRI = LBGI + HBGI: a measure of overall variability and risks of hypo- and hyperglycemia	x	x	x	

Category	Endpoints	24-Hour	Daytime ¹	Nighttime ²	Breakfast ³
Between-day	CV	x	x	x	
	SD	x	x	x	
	MODD	x	x	x	
Overall ⁶	CV	x	x	x	
	SD	x	x	x	
	IQR	x	x	x	
	LBGi	x	x	x	
	HBGI	x	x	x	
	BGRI	x	x	x	
Highest Postprandial Glucose					
	Time from start of meal to the highest postprandial glucose level (minutes) within 3 hours after breakfast				x
	Highest postprandial glucose level within 3 hours after breakfast				x
Other					
	Duration (in minutes) of each individual hypoglycemic episode (defined as at least 10 consecutive minutes <50, <60, and ≤70 mg/dL [2.8, 3.3, and 3.9 mmol/L])	across all hypoglycemic episodes with duration at least 10 consecutive minutes			

Abbreviations: AUC = area under curve; BGRI = blood glucose risk index; CGM = continuous glucose monitoring; CV = coefficient of variation; HBGI = high blood glucose index; IQR = interquartile range; LBGi = low blood glucose index; MAGE = mean amplitude of glycemic excursions; MODD = mean of daily differences; SD = Standard deviation.

Note:

- ¹ Daytime: 0600 hours to midnight (06:00:00-23:59:59 on the 24-hour clock).
- ² Nighttime: midnight to 0600 hours (00:00:00-05:59:59 on the 24-hour clock).
- ³ Breakfast is defined as the first “Carbs” event between 4 AM and 11 AM that is associated with an “Insulin” event within ±30 minutes.
- ⁴ All eCOA non-meal related correction doses excluding those confirmed as delivered via syringe for an unexplained hyperglycemia that leads to infusion set change, will be those delivered via the pump.
- ⁵ Time in ranges within 0-1 hour and 0-2 hours after breakfast
- ⁶ Overall variability refers to the variability calculated based upon all the CGM measurements collected across all valid days for each derivation period (e.g. 4-6 weeks relative to the start of each of the randomized treatment period).

To assess the glucose control over the course of approximately 72-hours of continuous insulin infusion, the duration and percentage of time in ranges (target, hypoglycemia or hyperglycemia)

and incremental AUCs after breakfast, will be derived based upon the CGM raw data collected on each of the infusion set catheter dwell days, including Day 1 (<0 and ≥ 24 hours), Day 2 (<24 and ≥ 48 hours) and Day 3 (<48 and ≥ 72 hours), and summarized by treatment group.

The glucose reduction rate and duration of each individual hypoglycemia episode will be analyzed by an MMRM model. The MMRM model will include the fixed effects of treatment, period, and sequence as fixed effects and patient as a random effect.

The glucose reduction rate and duration of each hypoglycemia episode will be analyzed by an MMRM model. The MMRM model will include the fixed effects of treatment, period, and sequence as fixed effects and patient as a random effect.

Hypoglycemia/hyperglycemia rates as measured by CGM data will be summarized for 30 days and 1 year / 100 years (hypoglycemia <50 mg/dl and hyperglycemia >300 mg/dl only). The rate of hypoglycemia and hyperglycemia will be compared between treatment groups using Wilcoxon signed-rank test.

The proportion of patients with at least 1 hypoglycemia/hyperglycemia event as measured by CGM data in each category (incidence) during a specific period after randomization will be analyzed using a generalized linear mixed model with options of the binomial distribution and logit link function with treatment, period, and sequence. The within-patient error will be modeled as an unstructured variance-covariance matrix. Prescott's exact test will be conducted as sensitivity analyses.

Other than that, all continuous variables (actual and change from baseline, if applicable) will be compared between LY900014 and insulin lispro at Week 6 using the MMRMs (Model 2) defined in Section 6.1.

In addition, the following standardized glucose summary reports from AGP will be generated, based upon the observed CGM measures during Weeks 4 to 6 of each randomized treatment period:

- 24-hour period at individual patient level
- 0-1 hours and 0-2 hours relative to breakfast starting time, excluding patients who have had the next Carb or Insulin event (if any is captured) at the treatment group level

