#### **9.1.4.1.1. Correction Boluses**

Patients will be instructed to enter the date, time, and dose for all non-meal-related correction bolus doses (those not associated with a meal or combined with a meal bolus) into the eCOA diary. This information is critical data for evaluating the primary objective of the study.

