#### **9.1.4.1.2. Infusion Set Changes**

The eCOA system will be used by patients to collect all infusion set changes, including date and time of change, designation of routine or premature change, primary reason for premature change (infusion set kinked, came out, or leaking; empty pump reservoir; infusion site pain or redness; pump occlusion alarm; suspected infusion set occlusion; other).

In the case of suspected infusion set occlusion, patients will choose or enter a new correction bolus from the eCOA diary that corresponds to the time of the suspected occlusion. They will then indicate if the correction bolus was given via pump or via syringe. If more than one correction bolus is given, patients should choose the first non-meal related correction bolus. This information is also critical in order to evaluate the primary objective of the study.

Investigators will review pump occlusion alarms, suspected infusion set occlusions, and premature infusion set changes with patients at each visit.

Any interruption of CSII will need to be documented in the eCRF. When patients resume use of pump following the interruption, the infusion set insertion should be entered as “routine” infusion set change in eCOA.

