**9.1.4.2. Troubleshooting Unexplained Hyperglycemia**

Investigators will review unexplained hyperglycemia troubleshooting and management with patients at Visit 2 and may repeat as necessary at subsequent visits. Troubleshooting guidelines for unexplained hyperglycemia management will be provided as a tool for patient use. A blood ketone meter and test strips will be provided to each patient to aid in hyperglycemia management. All episodes of unexplained hyperglycemia >250 mg/dL should be confirmed by SMBG using the study glucometer. Patients should check to ensure the pump is in place, the prior bolus dose was delivered, and the infusion set is in place without any leaks or kinks in the system. All non-meal-related correction boluses including date, time, and dose should be entered into eCOA. Glucose response to the correction bolus should be confirmed by SMBG in approximately 1 hour. Blood ketones should be tested with the meter provided when unexplained hyperglycemia occurs with blood glucose >250 mg/dL (13.9 mmol/L) or a pump occlusion alarm occurs with blood glucose >250 mg/dL (13.9 mmol/L). If blood ketones are positive (>0.6 mmol/L) or nausea and/or vomiting is present, the patient should inject the correction dose by syringe, change the insulin, reservoir, and infusion set, and continue to monitor BG every 1 to 2 hours until within range. If BG is not responding to correction and/or signs of DKA are present, the patient should go immediately to the nearest emergency room.

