Pump interruption is defined as patient is off pump due to pump malfunction and is temporarily using injection therapy. It does not include the condition where patient uses a syringe to inject a correction bolus dose while still on pump. Any interruption of CSII will need to be documented in the electronic case report form (eCRF). When patients resume use of pump following the interruption, the infusion set insertion should be entered as “routine” infusion set change in eCOA.

[figure not shown]

Figure ITSI.5.2. Flow chart for reporting infusion set changes.

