9.3. Interstitial Glucose Reduction Rate following a Correction Bolus via the Pump

The interstitial glucose reduction rate (mg/dl per minute and mg/dl per minute per unit of insulin dose) within 4 hours following a non-meal-related correction dose via the pump will be calculated by dividing the interstitial glucose reduction by the time it takes to first recover (≤ 180 mg/dL) from hyperglycemia after the correction dose. The interstitial glucose reduction rate will also be analyzed by sub-intervals of interstitial glucose levels at the time of the non-meal-related correction bolus: 180 to 250, 250 to 300, and >300 mg/dL (10 to 13.9, 13.9 to 16.7, and >16.7 mmol/L). The interstitial glucose levels at the time of the non-meal-related correction bolus, is defined as the most recent interstitial glucose within 1 hour prior to the correction bolus.

The non-meal related correction boluses delivered by pump will be derived through the following steps:

- Step 1: pull all correction boluses captured in eCOA;
- Step 2: exclude those correction boluses delivered through syringe;

- Step 3: exclude those associated with the last prior SMBG within 1 hour ≤ 180 mg/dl and the last post SMBG within 2 hours increases from prior SMBG. These correction boluses should not have been reported as non-meal related;
- Step 4: remove duplicate correction boluses. If 2 correction boluses are reported for the exact same time, only 1 correction bolus will be included;
- Step 5: if within 4 hours a second correction bolus is given before recovery (≤ 180 mg/dl), only the first non-meal-related correction bolus time will be used and the data after the second correction bolus will be censored. If the glucose never recovered to ≤ 180 mg/dL within 4 hours before any other correction boluses are given, the glucose reduction rate will be calculated by dividing the greatest glucose reduction within 4 hours before any other correction bolus, by the time it took to reach this level.

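### In endpoint 6 a syringe correction not linked to a suspected occlusion counts as pump-delivered, and SAP 9.3 Step 5 limits this but does not remove it

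*SAP*

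**What the plan says.** **What the diary collects.** Protocol 9.1.4.1.1: "Patients will be instructed to enter the date, time, and dose for all non-meal-related correction bolus doses". Route is not among the items. Protocol 9.1.4.1.2 adds: "In the case of suspected infusion set occlusion, patients will choose or enter a new correction bolus from the eCOA diary", and then "They will then indicate if the correction bolus was given via pump or via syringe". On which bolus to link: "If more than one correction bolus is given, patients should choose the first non-meal related correction bolus". Protocol 9.4.7 and SAP 5.1 describe the same procedure. A pump occlusion alarm, and a kinked, dislodged or leaking set, are separate reasons for a premature change. No route question is described for them.

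**Syringe corrections are foreseen.** Protocol 9.1.4.2 calls for a ketone test at unexplained hyperglycemia, or at an occlusion alarm, with glucose above 250 mg/dL. If ketones are positive or there is nausea or vomiting, "the patient should inject the correction dose by syringe, change the insulin, reservoir, and infusion set".

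**How the analysis classifies a dose.** Footnote 4 of SAP Table ITSI.6.8 takes all diary corrections, "excluding those confirmed as delivered via syringe for an unexplained hyperglycemia that leads to infusion set change, will be those delivered via the pump". SAP 9.3 states without limit: "Step 2: exclude those correction boluses delivered through syringe". Step 5 then handles a second correction within 4 hours and before recovery: the first bolus is the index and later data are censored.

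**The off-pump exclusion.** SAP 5.1 says of a pump interruption: "It does not include the condition where patient uses a syringe to inject a correction bolus dose while still on pump". These doses therefore stay in the data.

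**The concern.** Endpoint 6 is defined by route, but for most correction boluses the data described cannot confirm the route. Step 2 asks for every syringe dose to be removed, and footnote 4 shows that only one kind can be recognized. The remainder can arise when delivery through the set is in doubt, which is the situation this trial was set up to compare. If such doses enter as index boluses, a fall in glucose after an injection is scored as a response to pump delivery. The effect would weigh most where few boluses contribute, such as the sub-interval starting above 300 mg/dL. No planned analysis shows how far the result depends on the route assumption.

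**Working it through.** The plan gives no figure for this point. Its only reproducible planning number, 48 randomized, follows from 42/(1 − 0.12) = 47.7, and nothing here depends on it. The check is a trace of each type of correction through Protocol 9.1.4.1.1 to 9.1.4.2, footnote 4 and SAP 9.3.

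**Trace**

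1. *Suspected occlusion, first correction by syringe.* Route is asked and Step 2 removes the dose. Handled, subject to item 6.
2. *Pump bolus fails, then a recorded, unlinked syringe dose within 4 hours and before recovery.* The pump bolus is the index and Step 5 censors everything after the injection. The recovery is not credited to the pump. Handled.
3. *Set change for an alarm, or for a kinked, leaking or dislodged set, with a syringe dose as the first correction.* No route question is described, so the dose becomes an index pump bolus. Step 3 does not remove it, since that step needs a prior SMBG of 180 mg/dL or less. Not handled.
4. *Unlinked syringe dose more than 4 hours after a pump bolus.* It falls outside Step 5 and becomes an index pump bolus. Not handled.
5. *Syringe dose linked and flagged although it came second.* Step 2 deletes it before Step 5 runs. Read in order, it no longer censors the earlier pump bolus. Unclear.
6. *Flagged syringe dose first, then a pump bolus within 4 hours and before recovery.* With the syringe dose deleted at Step 2, the pump bolus becomes an index although the injection may still be acting. Not handled on a literal reading.
7. *Set change inside the 4-hour window.* No step censors there, so a fall after the new set is in place can be credited to a bolus given through the old one. Not handled.

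**Size**

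Let f be the share of index boluses that were really syringe doses, and k the ratio of the syringe to the pump reduction rate. The documents give neither. Both are assumptions here, with k from 0.5 to 2.

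Relative change in a treatment mean = f × (k − 1).

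For f, assume one misclassified dose per infusion set failure, at 0.44 or 2.0 failures per patient per 30 days. These are the two rates in the power statement that amendment (a) removed. They refer to a different event definition and serve only as a range. Assume also 0.5, 1 or 3 corrections a day, which is 21, 42 or 126 per 42-day period.

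- 0.44 × 42/30 = 0.62 failures: f = 0.62/126 = 0.5%, 0.62/42 = 1.5%, 0.62/21 = 2.9%.
- 2.0 × 42/30 = 2.8 failures: f = 2.8/126 = 2.2%, 2.8/42 = 6.7%, 2.8/21 = 13.3%.

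This is generous, because many failures would have no syringe dose or would fall under items 1 or 2. It does leave out kinked, leaking or dislodged sets, which are not in that rate.

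- f = 1%: −0.5% to +1%.
- f = 6.7%: −3.3% to +6.7%.

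Bias in the LY900014/lispro ratio, if the true ratio is 1, is [1 + f₁(k − 1)]/[1 + f₀(k − 1)] − 1, where f₁ is the share on LY900014 and f₀ the share on lispro.

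- f₁ = f₀, same k: 0.
- 3% against 1%: 0.985/0.995 − 1 = −1.0% (k = 0.5) to 1.03/1.01 − 1 = +2.0% (k = 2).
- 20% against 5%, an illustration of a stratum where rescue doses cluster: 0.90/0.975 − 1 = −7.7% to 1.20/1.05 − 1 = +14.3%.

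**The case against.** A reader might infer that every syringe correction is scored as a pump bolus, or that a failed pump bolus is credited with the recovery after a rescue injection. The documents do not support either reading. Doses confirmed as syringe are excluded. In the usual sequence the patient rechecks at about 1 hour, so a recorded injection falls inside 4 hours and Step 5 cuts off what follows. The failed pump bolus stays in with its own reduction rate. That objection stands in full for item 2 of the trace.

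The ordering problem in item 5 needs a patient to depart from the instruction to link the first bolus, and Step 5 speaks of any other correction bolus, which could be read to include syringe doses. The text is therefore ambiguous there rather than plainly wrong. Item 6 needs no departure from the linking instruction, although it too turns on reading the steps in order.

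The reporting flow chart, SAP Figure ITSI.5.2, is not shown, so a further route question cannot be ruled out. All the visible text points the other way, and footnote 4 itself treats syringe delivery as confirmed only for unexplained hyperglycemia leading to a set change.

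Endpoint 6 is also one of several secondary measures without multiplicity adjustment, and infusion set failure is measured directly by the primary endpoint. That lowers the stakes, but it does not make the route condition verifiable.

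**Conclusion.** The point holds in a limited form. Syringe corrections that are not linked to a suspected occlusion default to pump-delivered. Step 5 covers the common path, but leaves first-correction injections at an alarm or with a kinked, leaking or dislodged set, and unlinked injections more than 4 hours after a pump bolus. The order of Steps 2 and 5, and the absence of censoring at a set change, leave further gaps. Confidence in the gap is high on the visible text; confidence in its size is low.

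The size is unknown and probably small overall: about −1% to +2% in the treatment ratio for assumed shares of 3% against 1%. It could be larger above 300 mg/dL, but the −7.7% to +14.3% shown there rests wholly on assumed shares of 20% and 5%.

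It is tempting to conclude that the error hides a loss of pump effect for the insulin with more set failures. The documents do not support this: the sign depends on k, which is unknown, and equal shares with the same k give no bias. Nor do they say whether the injected dose is study insulin, so the only sure error is in the route.

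**What to change.** In SAP 9.3, apply Step 5 to all recorded corrections regardless of route, and only then remove the identified syringe doses (Step 2). State that any infusion set change also censors. Reword footnote 4 to say that route is confirmed only for linked boluses and is assumed to be the pump otherwise.

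Add a sensitivity analysis, with its window fixed before unblinding, that drops index boluses shortly before a premature set change for an alarm, kink, leak or dislodgement. It should not be the main rule, because it would also delete genuine failed pump boluses, possibly more of them on the insulin with more failures.

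Matching diary entries to the pump's bolus history would settle the route directly. However, the pump fields entered in Inform (Schedule of Activities, footnote r) are settings, totals and counts by bolus type, with no time-stamped corrections, so matching would need new data collection.

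The cost is SAP wording, a little more programming, and shorter follow-up for some boluses. Nothing changes for patients or sites.
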